5.2.3. Discrimination

Discrimination is the ability of the score to correctly identify patients with the outcome. The investigators will estimate the sensitivity, specificity, positive and negative likelihood ratio for the defined threshold of each score (ABC, TASH, BATT).

The likelihood ratio is the likelihood of a positive score in a patient with the outcome compared to the likelihood of a positive score in a patient without the outcome. The positive likelihood ratio is the ratio of sensitivity to 1-specificity. The negative likelihood ratio is the ratio of 1-sensitivity to specificity. A positive likelihood ratio of 10 or above will result in a large increase in the probability of the outcome. A negative likelihood ratio of 0.1 or less will result in a large decrease in the probability of the outcome.

The investigators will plot the Receiving Operating Characteristic (ROC) curve which is the sensitivity (true positives) on 1-specificity (false positives) for each defined threshold of each

score. An ideal score will reach the upper left corner (all true positive with no false positive). The investigators will estimate the area under the ROC curve (AUROC) that corresponds to the concordance statistic (C-Statistic) for binary outcome. A C-statistic of 1.0 shows perfect discrimination ability.

5.2.4. Calibration

Calibration is the agreement between observed and predicted outcomes. The investigators will mostly estimate calibration as the difference between the mean predicted and observed probabilities and the ratio of the predicted and observed number of events (P/O). The investigators will plot the observed and predicted probabilities of massive transfusion by decile of the score and with local regression based on LOESS algorithm. The investigators will estimate the calibration intercept and slope of the calibration plot as a measure of spread between predicted and observed outcome. Ideally, the intercept would be zero indicating that the predictions are neither systematically too low or too high and the slope would be 1.

Unfortunately, the investigators cannot estimate the calibration of the BATT score, because of its different outcome (death due to bleeding and not the massive transfusion as the TASH and ABC score). For the BATT, calibration will be assessed with the outcome of death due to bleeding or early death.

5.2.1.1 Efficacy analyses of secondary outcome

The investigators will perform the same analysis for secondary outcomes as the primary outcome.

5.2 Missing Data

Due to the retrospective aspect of the study based on a multicentric registry, the investigators expect to have some missing data for some prehospital and in-hospital predictors.

5.2.1. Imputation method

To estimate baseline risk for the full dataset, the investigators will replace missing predictors using multiple imputation by chained equations on sex, age, systolic blood pressure, respiratory rate, heart rate, Glasgow coma scale, Haemoglobin, base excess, type of injury (penetrating/blunt) Instable pelvis fracture and open/dislocated femur fracture with 20 imputed dataset. All analysis and results will be present in two subgroups: missing data imputed and missing data excluded.

5.2.2. Early deaths and early deaths with haemorrhage as a proxy for death due to bleeding

Because the investigators don't know if the Swiss Trauma Registry record the cause of death, the investigators expect some missing data about death due to bleeding as a secondary outcome. In case of missing data on secondary outcomes, the investigators will use early deaths and early deaths with evidence of haemorrhage as a proxy for death due to bleeding. Specifically, the investigators will included deaths from all causes within 12 hours of injury (excluding massive destruction of skull or brain; asphyxia, drowning and hanging are already excluded from the STR) and deaths between 12 to 24 hours with evidence of bleeding (Activation of massive transfusion protocol or blood within 6 hours or an abbreviated injury scale (AIS) diagnosis associated with haemorrhage: Blood loss >20%, Aorta [OR] Vena Cava [OR]carotid [OR]femoral [OR]Major arteries [OR]veins AND laceration, - Spleen [OR]liver [OR] Kidney [OR] Myocardium [AND] major laceration, major haemothorax, retroperitoneum haemorrhage).

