
Measurements and procedures:
	
Predictive Variables:
 
Demographics: Age, gender, type of accident, mechanism of Injury (penetrating/blunt), Hospital (anonymised by number), Date and time of accident.
 
Prehospital settings: Arrival on scene (paramedics, date/time and medics, date/time), type of transport: physician staffed ambulance/helicopter, Firsts clinical measures recorded: Systolic blood pressure (SBP), Respiratory rate (RR), Heart Rate (HR), Pulse Oximetry, Glasgow coma scale, temperature, cardiopulmonary reanimation, Drugs Use: Tranexamic acid (Date/time) and vasoactive, early death before arriving to the hospital.
 
In-hospital settings (trauma room): Hospital arrival (date/hour), Firsts measures: Systolic blood pressure (SBP), Respiratory rate (RR), Heart Rate (HR), Pulse Oximetry, Glasgow coma scale, temperature, cardiopulmonary reanimation, Biological parameters: haemoglobin, Platelets, lactates, Base excess, TP (sec and %), INR, PTT, Fibrinogen, Drugs use: Tranexamic acid (date/time), vasoactive, Vitamin K, Fibrinogen, Prothrombin complex concentrate, rFVIIa, Red blood cell (number in the first hour, date/hour of each Red blood cell), platelets units, fresh frozen plasma.
 
Imaging: type of imaging, results: positive or negative for free fluid, date/time of imaging.
 
Diagnosis: AIS final, ISS final, Medical past, use of anticoagulant/antiaggregant before trauma
 
Outcome: Date/time of death, Early death (<12 hours), Early death (<24 hours), number of red blood cell in 24 hours, Massive transfusion (defined as ≥ 10 red blood cells in the first 24 hours).
 
Depending of the availability of requested variables in the registry, we will ask for complementary variables.
 
Comparison:
 
Performance comparison of pre-existing scores (TASH, ABC and BATT scores) in term of overall performance, discrimination and calibration.
 
Evaluation of clinical utility and feasibility in prehospital settings and emergency admission.

Intervention:
	
Comparison of score performances (Overall performance, discrimination and calibration)

Control Intervention (if applicable):
	
No group controls

Number of Participants with Rationale:
	
The number of participants will depend of the Swiss Trauma Registry Database. We project to include 10'000 participants for our study. A post-hoc power calculation will be performed.

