
Study Duration:
	
11 months

Study Schedule:
	
From August 2020 to June 2021

Investigator(s):	
[name] Study Director Service des Urgences Centre hospitalier Universitaire Vaudois (CHUV) [name] [name] Email : [contact]
 
Doctor [name] Study Director Service des Urgences Centre hospitalier Universitaire Vaudois (CHUV) [name] [name] Email : [contact]
 
[name] Principal investigator Service des Urgences Centre hospitalier Universitaire Vaudois (CHUV) [name] [name] Email : [contact]

Study Centre(s):	
Multi-centre study including 12 Swiss Trauma Centre included in the Swiss Trauma Registry (Centre Hospitalier Universitaire Vaudois, Hôpitaux universitaire Genevois, Inselspital Bern, Universitätsspital Basel, Universitätsspital Zürich, Kantonsspital St. Gallen, Luzerner Kantonsspital, Kantonsspital Aarau, Kantonsspital Graubünden, Kantonsspital Winterthur, EOC – Ospedale Regionale di Lugano, Gesundheitsnetzwerk Wallis – Standort Sion)

Statistical Considerations:	
Comparison between scores:
 
 - Overall performance: Brier score - Discrimination: C-statistic, AUROC curve and calculation of likelihood ratio, sensitivity and specificity. - Calibration: Global calibration, calibration curve with intercept and slope calibration. 
Missing data: To estimate baseline risk for the full dataset, we will replace missing predictors using multiple imputation by chained equation.
 
Please referring to the Statistical Analysis Plan

GCP Statement:	
This study will be conducted in compliance with the protocol, the current version of the Declaration of Helsinki, the ICH-GCP or ISO EN 14155 (as far as applicable) as well as all national legal and regulatory requirements.

Study Procedure/Flowchart with Timelines: Study specific Examinations have to be clearly identified

1st step :Request database to the Swiss trauma registry, redacting the statistical analysis plan and study registration on Clinicaltrials.org (August-September 2020)

2nd step: Statistical Analysis (October 2020)

3rd step: Results (December 2020)

4th step: Publication

Storage of Data-and Samples for Future Research Aims: no**Ethical Considerations:**

1. Please describe the potential gain of new knowledge obtained with this study, and its meaning for patients/society.

Answer n°1:

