2.1 Background and rationale

Since the 2000s, many prognostic scores were developed to predict traumatic haemorrhage. Most of these studies were retrospectives based on registers. Due to missing data on death due to bleeding, these studies chose to predict the massive transfusion risk as a surrogate of haemorrhagic death. These scores include clinical parameters (vital signs), laboratory values (Haemoglobin, lactate, Base excess) and/or imaging (CT or ultrasound) values. The scores showing best performance are the Trauma Associated Severe Haemorrhage (TASH) score, developed and validated on the German register (DGU-Register) (1, 2) and the ABC score developed and validated in the United States of America (3, 4). The scores with variables are described on Figure 1,2.

However, the majority of these scores cannot be applied at the trauma scene due to the unavailability of laboratory and imaging values. Therefore, their clinical utility remains unclear. To overcome the need for diagnostic tests, authors have developed and recently validated a clinical prognostic score in identifying trauma patients with, or at risk of, significant haemorrhage based on predicted probabilities of death due to bleeding: BATT score (5). This score was developed from an international cohort using data from 271 Trauma Centres in 41 countries on 5 continents and uses first clinical parameters at initial assessment. The BATT score predicts death due to bleeding and has been validated on a large population in England and Wales. It could also predict massive transfusion, as a surrogate of haemorrhagic death, earlier at the trauma scene. Its feasibility and external validation would make its clinical utility superior to other scores while identifying a greater number of patients requiring early management.

Our study is an external validation of pre-existing prognostic scores of traumatic haemorrhages (TASH^{1,2}, ABC^{3,4} and BATT⁵ score) at different times of care (Scene of Injury, admission at the trauma room) in order to assess their overall performance, discrimination and calibration in the prediction of massive transfusion, and haemorrhagic death. The objective of the study is to assess a comparison of score performances (Overall performance, discrimination and calibration).

3. Study Methods

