4.3 Baseline patient characteristics

4.3.1 *Collected baseline patient characteristics*

The observational study is designed to record a set of demographical data, clinical examination in prehospital or in-hospital setting, in-hospital biochemical values and imaging variables for each included patient. The investigators will extract the data from the Swiss trauma registry (STR). The investigators plan to extract the biological parameters from the register at the trauma room stage. The clinical examinations will be the first measures at the pre and in-hospital stage. **Table 1** provides an overview of all variables requested from the registry before receiving the dataset.

4.3.2 *Descriptive summary of baseline patient characteristics*

The investigators will list general patient characteristics in a baseline characteristics table. Data will be presented as mean with standard deviation (SD) when normally distributed or as median with interquartile range in case of skewed data. Dichotomous and categorical data will be presented in proportions. **Table 2** provides a summary of potential baseline characteristics.

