5.2. Analysis methods

5.2.1. Efficacy analyses of primary outcome

First, the investigators will assess the accuracy (overall performance), discrimination and calibration of ABC, TASH and BATT score for the prediction of massive transfusion in trauma patients at the trauma scene and at the hospital admission.

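### The SAP's imputation list omits free fluid/FAST, so a patient without that result has no complete TASH or ABC score in any imputed dataset

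*SAP*

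**What the plan says.** SAP 5.2.1 (Imputation method) states the aim: "To estimate baseline risk for the full dataset, the investigators will replace missing predictors using multiple imputation by chained equations". It then lists sex, age, systolic blood pressure, respiratory rate, heart rate and Glasgow Coma Scale, and ends with "Haemoglobin, base excess, type of injury (penetrating/blunt) Instable pelvis fracture and open/dislocated femur fracture with 20 imputed dataset". That makes 11 variables. Neither free fluid nor any outcome is among them.

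The protocol synopsis places imaging under its predictive variables: "type of imaging, results: positive or negative for free fluid, date/time of imaging". Its statistical paragraph says "we will replace missing predictors using multiple imputation by chained equation", gives no list of variables, and refers the reader to the SAP. SAP Table 1 requests the CT or FAST free-fluid result, in the trauma-room column only. SAP 5.2 (Missing Data) warns that "the investigators expect to have some missing data for some prehospital and in-hospital predictors", without a rate.

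On timing, SAP 5.2.1 (Efficacy analyses of primary outcome) plans to assess "ABC, TASH and BATT score for the prediction of massive transfusion in trauma patients at the trauma scene and at the hospital admission", and Table 1 marks TASH and ABC in both the prehospital and the trauma-room columns.

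**The concern.** TASH and ABC are sums of items. If one item is missing and is neither imputed nor given a default, the sum does not exist. The imputation is meant to deliver results for the full dataset, yet its list would leave a gap in two of the three scores being validated.

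Two things could follow, and the SAP does not choose between them. Patients without a free-fluid result could drop out of the imputed analysis of TASH and ABC, which would then rest on a selected subset. Or the analyst could score the blank as negative, which understates the risk of any such patient who did have free fluid. Either choice would be made after the missingness is visible, which works against the SAP's stated wish to avoid data-driven results.

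**Working it through.** **Step 1: compare the item lists.** Score items come from SAP Figures 1 and 2, imputed variables from SAP 5.2.1 (Imputation method).

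| Item | TASH maximum points | ABC points | On imputation list? |
|---|---|---|---|
| Haemoglobin | 8 | – | yes |
| Base excess | 4 | – | yes |
| Systolic blood pressure | 4 | 1 | yes |
| Heart rate | 2 | 1 | yes |
| Free fluid / FAST | 3 | 1 | **no** |
| Unstable pelvic fracture | 6 | – | yes |
| Open or dislocated femur fracture | 3 | – | yes |
| Male sex | 1 | – | yes |
| Penetrating mechanism | – | 1 | yes |

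TASH maximum: 8 + 4 + 4 + 2 + 3 + 6 + 3 + 1 = 31. ABC maximum: 4. Both agree with the upper limits of the score categories in Table 2 (18-31 and 2-4), so the item lists are complete. The imputation list covers 7 of 8 TASH items and 3 of 4 ABC items. Its other three variables (age, respiratory rate, Glasgow Coma Scale) belong to neither score.

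**Step 2: what depends on the complete score.** The AUROC uses the full score, so it is affected for both TASH and ABC. The Brier score and calibration need a predicted probability. Figure 1 supplies one for TASH. Figure 2 supplies none for ABC, so those two measures are affected here for TASH only.

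Classification at a cut-off suffers less. ABC at 2 or more is undetermined only for patients with exactly 1 point from the other items. The Table 2 TASH split at 18 is undetermined only for those with 15 to 17 points from the other items.

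**Step 3: size if a blank is scored as negative.** For a patient who has free fluid and k points from the other items, the loss in Figure 1 probability is P(k + 3) − P(k):

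| k | P(k), % | P(k + 3), % | Loss, percentage points |
|---|---|---|---|
| 9 | 6 | 14 | 8 |
| 10 | 8 | 18 | 10 |
| 11 | 11 | 23 | 12 |
| 12 | 14 | 29 | 15 |
| 13 | 18 | 35 | 17 |
| 14 | 23 | 43 | 20 |
| 15 | 29 | 50 | 21 |
| 16 | 35 | 57 | 22 |
| 17 | 43 | 65 | 22 |
| 18 | 50 | 71 | 21 |
| 19 | 57 | 77 | 20 |
| 20 | 65 | 82 | 17 |

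The range is 8 to 22 points. For ABC, a true score of 2 becomes 1 and the patient moves from high risk to low risk.

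**Step 4: size if the patient is dropped.** The SAP anticipates 10,000 participants and gives no missingness rate. If a fraction m lacks the result, 10,000 × m patients have no complete TASH or ABC score. For an assumed m of 5% this is 500; for an assumed m of 40% it is 4,000. These are illustrations. The documents give no basis for a figure for the change in AUROC.

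**Step 5: the scene.** Table 1 requests haemoglobin (8), base excess (4) and free fluid (3) in the trauma room only: 8 + 4 + 3 = 15 of 31 TASH points. For the laboratory items SAP 4.3 agrees: "The investigators plan to extract the biological parameters from the register at the trauma room stage". Two of these three items are already on the imputation list, so the scene gap has a different cause and adding free fluid does not close it.

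**The case against.** **The intent is clear.** Both documents say that missing predictors will be replaced, and the protocol counts free fluid as a predictor. The omission is probably a drafting slip. That stands as an account of how it arose. But the protocol gives no list and defers to the SAP, whose explicit list is what a programmer will follow.

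**The effect may be trivial.** This stands. No rate is given, and if almost every patient has a recorded result, nothing of note changes at admission. A reader might infer that the planned AUROCs are materially biased; the documents do not support that, because any estimate needs an assumed missingness rate and pattern.

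**Imaging not done can be read as negative.** No section says so, and the protocol codes results only as positive or negative. How to code imaging not performed is a detail with arguments on both sides. Its absence is not an error in itself.

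**A complete-case analysis is also promised**, in SAP 5.2.1 (Imputation method) and in Subgroup 5 of SAP 5.3. That is a useful second analysis, but it does not repair the imputed one, and the SAP does not say which items must be complete.

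**Stronger readings that do not hold.** A reader might infer that TASH and ABC will be compared with BATT on different patients. BATT's items are not set out in the documents, so this cannot be checked. A reader might also infer that the outcome is excluded from the imputation model. The SAP is silent; it does not exclude it. Finally, a reader might conclude that no patient at the scene can reach the 18-31 TASH category. That requires scoring unavailable items as zero, a rule stated nowhere, and the background section itself acknowledges that "the majority of these scores cannot be applied at the trauma scene due to the unavailability of laboratory and imaging values".

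**Conclusion.** The point holds as a gap in the imputation specification that should be closed before the data are analysed. Free fluid/FAST is the only TASH or ABC item absent from the list. As written, the imputed AUROCs for TASH and ABC, and the TASH Brier score and calibration, cannot cover the full dataset unless every patient has a free-fluid result. That follows from the text alone.

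The consequence for an individual patient is fixed by the SAP's own figures: 8 to 22 percentage points of TASH probability for other-item totals of 9 to 20, or one ABC point that can cross the cut-off, if a true positive is scored as negative. The consequence for the study results depends on a missingness rate that the documents do not give, and ranges upward from negligible.

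Separately, the plan to assess TASH and ABC at the scene conflicts with requesting 15 of the 31 TASH points, and the FAST item of ABC, only in the trauma room. Those passages must be reconciled.

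This conclusion rests on the SAP from section 1.4 onwards; its earlier pages were not available to me, though a missing-data rule there is unlikely.

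**What to change.** In SAP 5.2.1 (Imputation method):

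- Add free fluid (CT or FAST) to the imputed variables. All TASH and ABC items are then covered.
- State that massive transfusion and the available death outcomes are predictors in the imputation model. Leaving the outcome out weakens the association between imputed items and outcome and tends to lower the AUROC. Death due to bleeding, or its proxy, enters only if obtained.
- Compute each score from its components within each of the 20 datasets.
- Compare the scores on the same patients.

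Separately, reconcile the scene assessment with Table 1 by stating what is computed for TASH and ABC at the scene: assessment at admission only, a reduced score labelled as such, or trauma-room values carried back.

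The cost is a few lines of text and a slightly larger imputation model. Free fluid, massive transfusion and early death are already requested in Table 1, so the imputation changes need no further data request.

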
Objective(s):
	
 - External validation of pre-existing prognostic scores of traumatic haemorrhages at different times of care (Scene of Injury, admission at the trauma room) in order to assess their overall performance, discrimination and calibration in the prediction of massive transfusion and haemorrhagic death. - Comparison of score performances (Overall performance, discrimination and calibration).

Outcome(s):
	
Primary study outcome :
 
 - Massive transfusion defined by a transfusion equal to or greater than 10 Red blood cell (RBC) / 24 hours or ≥ 3 RBC in the first hour if available in the Swiss Trauma Registry. 
Secondary study outcome :
 
 - Death due to bleeding (if available in the registry) - Early death (< 24 hours) - Coagulopathy at admission defined by INR > 1.2, quick TP < 70% or Fibrinogen < 1.5 g/L (6,7,8)

Study design:
	
Observational non-interventional study based on a multicentric anonymized registry

Inclusion / Exclusion criteria:	
Study population: All adult trauma patients treated at twelve Swiss trauma centres Level I from 01.01.2015 to 31.12.2019 with eligible criteria of the Swiss Trauma Registry (STR) are included. All data from the register are anonymised without any access to medical files. The identity of the trauma patients, date of birth, address and trauma scene location are unknown (as mandatory by the swiss law: Art. 2 ORH).
 
Inclusion criteria:
 
- Age > 16 years old- ISS (Injury Severity Score) ≥ 16 and/or AIS head (Abbreviated Injured scale) ≥ 3 
Exclusion criteria:
 
- Age < 16 years old- ISS < 16 and or AIS < 3- Isolated Burns (including electric shock) or if the burn is clearly the primary injury- Patients arriving at the trauma room with no sign of life and no diagnostic/therapeutic measures have been initiated for them- Choking or hanging patient without any other injury.- Drowning patients
--	---

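### If cause of death is not recorded, the bleeding-death proxy admits deaths before 12 h without evidence of bleeding, and BATT may also be calibrated on all-cause early death; both can bias BATT calibration

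*SAP*

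**What the plan says.** The proxy is defined in the SAP's Missing Data part, in the second of two sections numbered 5.2.2. It is a fallback, written because "the investigators don't know if the Swiss Trauma Registry record the cause of death". The condition is: "In case of missing data on secondary outcomes, the investigators will use early deaths", together with early deaths showing haemorrhage, in place of death due to bleeding. It has two windows:

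- **Up to 12 h:** "deaths from all causes within 12 hours of injury", "excluding massive destruction of skull or brain". No AIS code or severity cut-off defines this exclusion, and no evidence of bleeding is needed.
- **12 to 24 h:** "deaths between 12 to 24 hours with evidence of bleeding", where evidence means massive transfusion protocol activation, blood within 6 h, or a listed AIS haemorrhage diagnosis.

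Entry to the cohort (Protocol synopsis, inclusion criteria; SAP 4.2.1) is "ISS (Injury Severity Score) ≥ 16 and/or AIS head (Abbreviated Injured scale) ≥ 3".

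SAP 5.2.4 declines to calibrate BATT on massive transfusion because BATT predicts another outcome. It then says: "For the BATT, calibration will be assessed with the outcome of death due to bleeding or early death". SAP 5.2.1.1 applies the primary-outcome analyses to every secondary outcome.

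**The concern.** The two windows use different standards, and the looser one covers the earlier deaths. A patient admitted on head AIS alone who dies of brain injury at 8 h, without what the SAP means by massive destruction, is counted as a bleeding death. The same death at 14 h is not, unless evidence of bleeding is found.

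The calibration section has a related inconsistency. Massive transfusion is ruled out for BATT because it is a different outcome. All-cause early death is also a different outcome, with neither a bleeding criterion nor a head-injury exclusion, yet it is allowed. No rule says which target applies when.

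Haemorrhagic death is a stated study objective and is the outcome BATT predicts. If cause of death is missing, BATT calibration rests wholly on the proxy or on early death. A good score could then look poor, or errors in the proxy could cancel and hide a real fault. AUROC and Brier comparisons of all three scores on this outcome use the same events.

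**Working it through.** The documents give no event rate, non-bleeding share or AUROC, so there is no figure of the plan's own to reproduce. Every input below is assumed and the results are illustrative.

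**1. P/O for a score that is truly calibrated to bleeding death**

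Let B be the true bleeding deaths, s the fraction of them the proxy captures, f the share of proxy deaths not due to bleeding, and O the number of proxy deaths. Predicted events equal B. Since s·B = (1 − f)·O, it follows that P/O = B/O = (1 − f)/s.

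| f | s = 1.00 | s = 0.85 |
|---|---|---|
| 0% | 1.00 | 1/0.85 = 1.18 |
| 10% | 0.90 | 0.90/0.85 = 1.06 |
| 20% | 0.80 | 0.80/0.85 = 0.94 |
| 40% | 0.60 | 0.60/0.85 = 0.71 |
| 60% | 0.40 | 0.40/0.85 = 0.47 |

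The two errors cancel when f = 1 − s, which is 15% at s = 0.85. Below that share the score appears to over-predict; above it, to under-predict.

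**2. Intercept and slope**

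In a logistic simulation (400,000 patients, bleeding-death rate 2% or 3%, all bleeding deaths captured), a perfectly calibrated score gave:

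| f | Calibration-in-the-large | Slope, head deaths unrelated to score | Slope, head deaths related to score |
|---|---|---|---|
| 20% | about +0.25 | about 0.78 | about 0.94 |
| 40% | about +0.58 | about 0.58 | about 0.87 |
| 60% | about +1.05 | about 0.39 | about 0.81 |

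The targets are 0 and 1. The slope depends heavily on whether the score also tracks head deaths.

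**3. Ranking on this outcome**

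Against a mixed case group, AUROC = (1 − f)·AUROC(bleeding) + f·AUROC(non-bleeding). Suppose score B leads A by d on bleeding deaths and A leads B by e on non-bleeding deaths. The order changes at f = d/(d + e). With d = 0.04:

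- e = 0.05: 0.04/0.09 = 44%
- e = 0.10: 0.04/0.14 = 29%
- e = 0.25: 0.04/0.29 = 14%
- e = 0: the order does not change.

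**4. Is a stricter version feasible?**

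SAP Table 1 requests AIS codes, red cells with number and time, and date and time of death. Activation of the massive transfusion protocol is not in Table 1.

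**The case against.** **The proxy is a fallback for a secondary outcome.** This stands. If cause of death is recorded, the proxy is not needed, and the primary comparison on massive transfusion is untouched either way. The allowance for early death in 5.2.4, however, carries no such condition. It might be read as shorthand for the proxy, but SAP 5.1 lists early death under 24 h as an outcome of its own, so the literal reading is all-cause death.

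**The looser early window has a rationale.** SAP 4.4 notes that some patients die before they can receive 10 units, and the Discussion mentions survival bias. Demanding blood or a coded lesion before 12 h could lose the fastest bleeders. Transfusion evidence also overlaps with massive transfusion, the outcome TASH and ABC target. Both points stand: they argue against replacing the proxy, not against a second version beside it.

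**The isolated severe TBI subgroup already addresses this.** In part only. It is planned if sample size permits, does not redefine the outcome, and leaves non-bleeding deaths in patients with multiple injuries where they are.

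**Stronger readings.** A reader might infer that BATT must appear to predict too low. That holds only if the proxy misses few bleeding deaths; it leaves out those after 24 h and those at 12–24 h without listed evidence.

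A reader might also infer that the proxy reverses the ranking of scores. One can build such a case: AUROC for bleeding death 0.847 without a head-injury item and 0.815 with one, becoming 0.673 and 0.758 at a 50% non-bleeding share. But those figures imply AUROCs for head deaths of 0.50 (0.5 × 0.847 + 0.5 × 0.50 = 0.673) and about 0.70 (0.5 × 0.815 + 0.5 × 0.70 = 0.758). TASH and ABC both contain blood pressure and heart rate, so no association at all is an extreme choice. The documents do not list the BATT items. Age, respiratory rate and Glasgow coma scale are imputed but appear in neither TASH nor ABC, which suggests that BATT uses them but does not prove it.

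**Conclusion.** The concern holds in a conditional form. If cause of death is unavailable, the proxy can admit non-bleeding deaths before 12 h, and 5.2.4 permits a calibration target that conflicts with its own reasoning. Either can make a well-calibrated BATT look miscalibrated. At non-bleeding shares of 20% to 60%, P/O would run from 0.80 to 0.40 with full capture and from 0.94 to 0.47 with 85% capture. The share and the capture rate are both assumed, and at low shares the error can change sign.

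A change of ranking on this secondary outcome is possible but not demonstrated; it needs one score to predict non-bleeding deaths better than another. Nor do the documents say what fraction of the cohort is head-injured; they show only that head AIS alone is enough for entry. The change is worth making before the data arrive, but the point does not threaten the primary analysis.

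**What to change.** 1. Keep the current proxy. Pre-specify a second, strict version that applies the SAP's listed haemorrhage evidence (AIS codes, red cells within 6 h) to deaths before 12 h as well.
2. Report BATT calibration, and the discrimination of all three scores, under both versions as a bracket. Neither should be the sole target: the current version may over-count, while a strict version that missed 15% of bleeding deaths and was otherwise clean would give P/O of 1.18.
3. In SAP 5.2.4, remove early death as a calibration target for BATT. In 5.2.1.1, state that BATT calibration is not assessed on early death, coagulopathy or any other outcome it does not predict. Keep early death for discrimination.
4. Do not remove deaths by the isolated severe TBI definition in SAP 5.3 until its and/or is resolved. Read as or, it would label a patient with severe abdominal injury but lower-extremity AIS below 4 as isolated TBI, and true bleeders could be dropped.

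The cost is one recoded outcome, mostly from variables already requested, and two edited sentences. Protocol activation would have to be requested in addition or left out of the strict rule. The strict version may miss rapid bleeders who died before transfusion or coding, which is why both are shown.
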